6.4 Patient and Clinician Selection

Since this evaluation is part of a quality improvement initiative, we will include 220 patients who may benefit from medication optimization. These patients will be identified using a report developed in the EHR. The same report will identify the “target clinician” for each eligible patient. A patient’s target clinician is defined as, in order of descending priority, either a (non-electrophysiologist) Michigan Medicine cardiologist (excluding TAVI visits) who has seen the patient in the prior year (if one exists), or else a Michigan Medicine PCP for the patient, or else the patient’s clinician of record for the anticoagulation monitoring service.

All target clinicians will be randomized to receive CNNF or usual care. Eligibility will be determined based on information in the electronic health record. All participants will be screened for eligibility in the week prior to study entry.

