8 END-OF-INTERVENTION/END-OF-STUDY

8.1 Discontinuation of Intervention

The QI strategies will not be delivered to patients who discontinue warfarin therapy or are closed to the anticoagulation monitoring service between the time of randomization and the

anticipated date of QI strategy delivery. Patients who discontinue warfarin therapy or are closed to the anticoagulation monitoring service after QI strategy delivery but before week 7-10 will not be assessed by phone at week 7-10, though chart review will still be completed for these patients. The QI strategies will additionally not be delivered to patients whose target clinician on the report changes between the time of randomization and the anticipated date of QI strategy delivery. However, patients whose target clinician changes after QI strategy delivery but before week 7-10 will still be assessed at week 7-10.

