9 STUDY ASSESSMENTS AND PROCEDURES

9.1 Eligibility Assessment

All eligible patients will be identified using a MiChart workbench report prior to the start of the study. Eligibility will be assessed based on information in the EHR. Each week, it is anticipated that 42 patients will be randomized to receive either CNNF or usual care, and that 21 will have CNNF directed at their target clinicians. Each anticoagulation nurses will deliver CNNF to up to 4 patients each week but may deliver CNNF to fewer some weeks depending on staffing. At the start of each week, eligibility will be re-assessed for patients anticipated to receive the QI strategy in the coming week.

Similarly, clinician eligibility will be determined at the start of the trial and at the beginning of each week to ensure that only actively practicing Michigan Medicine clinicians are included.

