11 STATISTICAL CONSIDERATIONS

11.1 Sample Size Determination

The study is powered to have 90% power to identify a difference between usual care and CNNF with a two-sided 5% type I error. We estimate that the rate of medication optimization will be 5% with usual care and 35% with CNNF. In the pilot study, we observed substantial variation at the clinician-level in whether clinicians responded to the notification messages at all. In our sample size estimates, we therefore assumed a high-level of correlation in the outcome for patients within clinician clusters (ICC=0.95). While our clinician population includes providers with 1-32 patients, if a clinician is selected to participate who has more than 4 patients (27/156), we will

randomly select 4 of their patients to participate in order to avoid overwhelming some clinicians with a large number of notifications in a short period of time. Therefore, capping the 27 providers who have more than 4 participants, there is a coefficient of variation=0.62 (calculated using preliminary data) of the number of patients per provider and an average of 2 participants per clinician. For 90% power to detect the 30% difference between interventions, we require 44 clinicians/arm and 176 total patient participants. We will assume a 20% dropout or ineligibility rate, so we plan to increase the N (176/0.8). This results in a final N of 220, equating to 110 participants and 55 clinicians per arm.

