11.2 General Statistical Approach

For the primary and secondary endpoints, an intention-to-treat analysis approach will be used.

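### Patients whose target clinician changes after randomisation but before delivery have no stated follow-up or analysis rule, and their outcomes are probably lost mainly in the CNNF arm

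*Combined protocol and SAP*

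**What the plan says.** - **How the target is set.** Section 6.4 ranks a non-electrophysiology cardiologist seen within the past year first, then a Michigan Medicine PCP, then the clinician of record. An EHR report identifies the target. Section 7.3 randomises by that clinician, so the target fixes both cluster and arm.
- **Change before delivery.** Section 8.1 withholds the QI strategy from "patients whose target clinician on the report changes between the time of randomization and the anticipated date of QI strategy delivery". It does not say whether these patients are called, chart-reviewed or analysed.
- **Change after delivery.** The next sentence, introduced as a contrast, says that "patients whose target clinician changes after QI strategy delivery but before week 7-10 will still be assessed at week 7-10".
- **Who is called.** The Study Description in the Synopsis (1.1) ties the phone survey to patients whose clinicians actually received CNNF or usual care.
- **Weekly checks.** Section 9.1 re-checks patients who are due to receive the strategy that week. It also says that "clinician eligibility will be determined at the start of the trial and at the beginning of each week", so that only clinicians in active practice are included. The clinician check is not limited to one arm.
- **Analysis.** Section 11.2 states: "For the primary and secondary endpoints, an intention-to-treat analysis approach will be used". The imputation text in 11.5 addresses patients who could not be contacted, who declined, or who called back after week 10. It also keeps in the primary analysis patients who report having been ineligible at baseline. It does not mention patients undelivered under 8.1.

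**The concern.** Cluster membership should be a baseline property, settled when the clinician is randomised. Here it can change afterwards without any treatment event: a cardiology visit passes the one-year mark, or the patient sees a new cardiologist or acquires a new PCP. If staff follow 8.1 as it most naturally reads, a CNNF patient whose target changes before delivery gets no message and no call. A usual-care patient with the same change has no delivery date to trigger the rule, and stays in.

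That would be a post-randomisation exclusion acting on one arm. The CNNF patients lost would be ones who received no message, so their absence would tend to raise the observed CNNF rate. If patients whose target changes also differ in prognosis, one-arm removal would leave two groups that are no longer comparable. The weekly clinician check raises a related issue in either arm, because a clinician found inactive after allocation could take a whole cluster out.

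**Working it through.** **1. The plan's own figure.** Section 11.1 gives a "two-sided 5% type I error", 90% power, the assumption that "the rate of medication optimization will be 5% with usual care and 35% with CNNF", ICC 0.95, coefficient of variation 0.62 and a mean of 2 patients per clinician.
- Unpooled two-proportion formula: (1.960 + 1.282)² × (0.05 × 0.95 + 0.35 × 0.65) / 0.30² = 32.1 per arm.
- Design effect: 1 + [(1 + 0.62²) × 2 − 1] × 0.95 = 2.680.
- 32.1 × 2.680 = 86.1 patients, or 43.03 clinicians, rounded up to 44 per arm. That is 176 patients in total, and 176/0.8 = 220.

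The stated sample size reproduces exactly. This point does not turn on a sample-size error.

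**2. What happens to these patients, passage by passage.**
- Delivery: withheld (8.1, stated).
- Call: not stated. The contrast in 8.1 and the Synopsis wording both point to no call.
- Arm: not stated. Section 5.2 gives the wait-list group the strategy only at study completion, and the patient re-check in 9.1 concerns those due for delivery. Both point to CNNF only. Against this, 7.1 lists usual care among the strategy descriptions, and 7.2.1 speaks of all patients receiving the strategy to which they were randomised.
- Missing outcome: not covered by 11.5.

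**3. Size if they are dropped.** Let f be the share of CNNF patients undelivered for this reason and q their rate of medication optimisation. The rate among those kept is 35%; the rate as randomised is 35(1 − f) + q·f. The overstatement is f × (35 − q) points. With q = 5%, the plan's usual-care rate, this is 30 × f.

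The documents give neither f nor the interval from randomisation to delivery. As an assumption, suppose annual cardiology visits spread evenly over the year and a wait of 1 to 4 weeks:

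| Wait | f | CNNF patients of 110 | Rate as randomised | Overstatement |
|---|---|---|---|---|
| 1 week | 1/52 = 1.9% | 2.1 | 34.4% | 0.6 points |
| 2 weeks | 2/52 = 3.8% | 4.2 | 33.8% | 1.2 points |
| 4 weeks | 4/52 = 7.7% | 8.5 | 32.7% | 2.3 points |

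The direction depends on q: the overstatement vanishes at q = 35% and reverses above it.

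**4. Power if they are kept as randomised.** Using the formula and design effect of step 1, with q = 5%, an illustrative f of 5% gives a CNNF rate of 33.5%. Power falls from 90.6% to 88.1% with 88 patients per arm assessed, or from 95.6% to 94.0% with 110 per arm.

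**The case against.** The strongest reply is that the protocol nowhere says these patients go uncalled. Where 8.1 means no call it says so, for patients who stop warfarin or leave the service after delivery. The contrast sentence could simply set continued follow-up against non-delivery. Section 6.4 screens all participants in the week before entry, in both arms. Non-receipt is what intention-to-treat analysis is designed to handle, and the protocol commits to it.

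Much of this stands. A reader might infer that the protocol plainly excludes these patients, that it does so in the CNNF arm alone, and that withholding delivery contradicts 11.2. The documents do not support any of these as stated rules. The missing call and the CNNF-only trigger are inferences, the clinician check covers both arms, and an undelivered patient can be analysed as randomised.

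The size is also open to challenge. Section 5.2 describes weekly randomisation, so the wait may be a week or less, although 5.4 allows patients in one cluster to enter at different times. The one-year look-back applies only to cardiologist targets, and the next visit to the same cardiologist renews it. For that mechanism, the 4/52 figure is nearer an upper bound than a central estimate. New visits could add to it, by an amount the documents do not give.

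What remains is that no section says how these randomised patients are followed or analysed, and the most natural reading loses their outcomes mainly in one arm.

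**Conclusion.** The point holds as a gap that probably acts as an arm-specific loss of outcomes, not as a written exclusion rule. Sections 8.1 and 9.1 need to be reconciled with 11.2 and 11.5.

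The likely effect is modest: 0.6 to 2.3 points of overstatement, on the assumptions of a 1- to 4-week wait, undelivered patients responding at 5%, and their being dropped from CNNF. Against a planned 30-point difference this is unlikely to change the conclusion. It should still be corrected, because the correction is cheap and because an undefined post-randomisation loss weakens the intention-to-treat claim whatever its size.

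**What to change.** In 6.4, 8.1 and 9.1:
- Take the target clinician, the cluster for analysis and clinician eligibility from one report run before randomisation.
- State that a later change of target clinician or clinician status, or non-delivery for that reason, does not remove a patient from assessment or analysis.
- Attempt the week 7-10 call, counted from entry week, and the chart review for these patients in both arms.

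In 11.2 and 11.5:
- Analyse these patients in the cluster and arm originally assigned.
- Extend the missing-data rule to any of them not called.
- Report target changes and non-delivery by arm.

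Two things are left as they stand: whether the message is delivered after a target change, and the separate no-call rule for patients who stop warfarin or leave the service.

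The cost is a wording amendment and a few extra calls of about 5 minutes each. The downside is a slightly less favourable CNNF rate, because undelivered patients stay in the comparison.

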8.2 Participant Discontinuation/Withdrawal from the Study

Patients who wish not to participate in the phone survey at week 7-10 will have the phone survey discontinued.

8.3 Lost to Follow-Up

For patients unable to be reached for the phone survey at week 7-10, chart review will still be performed.

9 STUDY ASSESSMENTS AND PROCEDURES

9.1 Eligibility Assessment

All eligible patients will be identified using a MiChart workbench report prior to the start of the study. Eligibility will be assessed based on information in the EHR. Each week, it is anticipated that 42 patients will be randomized to receive either CNNF or usual care, and that 21 will have CNNF directed at their target clinicians. Each anticoagulation nurses will deliver CNNF to up to 4 patients each week but may deliver CNNF to fewer some weeks depending on staffing. At the start of each week, eligibility will be re-assessed for patients anticipated to receive the QI strategy in the coming week.

Similarly, clinician eligibility will be determined at the start of the trial and at the beginning of each week to ensure that only actively practicing Michigan Medicine clinicians are included.

9.2 Assessment of the Primary Endpoint

The primary endpoint, defined as the proportion of patients for whom medication optimization was achieved (defined as either discontinuation of all antiplatelet therapy or initiation and

adherence to a proton pump inhibitor) will be determined by patient reported medication use at week 7-10. Up to three attempts will be made to contact patients by phone over the course of 4 weeks to assess the primary endpoint. The phone call is anticipated to take not more than 5 minutes. With calls 1 and 3, a brief message will be left stating the research assistant's name and affiliation with the anticoagulation clinic and asking the patient to call back at their earliest convenience. A script has been developed to guide the phone survey. If the patient self-reports any use or non-use of medications that contradicts the information in their MiChart medication list, the research assistant will send a message to the patient's anticoagulation clinic nurse so that the nurse can reconcile the chart. No remuneration will be offered with this patient assessment. We request a waiver of informed consent for this patient phone survey.

There will be no assessments that require physical exams, radiology, biological specimens or laboratory evaluations.

9.3 Assessment of the Secondary and Exploratory Endpoints

The secondary and exploratory endpoints outlined in section 4 of this protocol document will be determined based on chart review, as well as patient self-reported data from the week 7-10 phone survey.

10 ADVERSE EVENTS

Since this trial constitutes a quality improvement trial intended to improve the use of evidence-based practices to reduce bleeding in patients using AAT, and since all decisions regarding changes in drug treatment will be made by patients' own clinicians as part of usual care, the study will not proactively monitor for adverse events. No experimental drug is being investigated. However, any adverse events that are identified will be logged in an adverse event database.

11 STATISTICAL CONSIDERATIONS

11.1 Sample Size Determination

The study is powered to have 90% power to identify a difference between usual care and CNNF with a two-sided 5% type I error. We estimate that the rate of medication optimization will be 5% with usual care and 35% with CNNF. In the pilot study, we observed substantial variation at the clinician-level in whether clinicians responded to the notification messages at all. In our sample size estimates, we therefore assumed a high-level of correlation in the outcome for patients within clinician clusters (ICC=0.95). While our clinician population includes providers with 1-32 patients, if a clinician is selected to participate who has more than 4 patients (27/156), we will

randomly select 4 of their patients to participate in order to avoid overwhelming some clinicians with a large number of notifications in a short period of time. Therefore, capping the 27 providers who have more than 4 participants, there is a coefficient of variation=0.62 (calculated using preliminary data) of the number of patients per provider and an average of 2 participants per clinician. For 90% power to detect the 30% difference between interventions, we require 44 clinicians/arm and 176 total patient participants. We will assume a 20% dropout or ineligibility rate, so we plan to increase the N (176/0.8). This results in a final N of 220, equating to 110 participants and 55 clinicians per arm.

11.2 General Statistical Approach

For the primary and secondary endpoints, an intention-to-treat analysis approach will be used.

11.3 Descriptives

We will calculate descriptive statistics (means, standard deviations, range and proportions) for all patient variables for the sample in total, by main effect (CNNF vs usual care) with and without controlling for clinician.

11.4 Hypotheses

For the primary endpoint, we hypothesize that the CNNF compared to usual care will be associated with a higher probability of medication optimization.

11.5 Analysis of the Primary Endpoint(s)

We will use generalized linear mixed effects modeling (logit link) to estimate the odds of medication optimization at week 7-10. This model will include fixed effects for CNNF (vs. usual care), target provider specialty and size, and a random effect for clinician to account for the clustering of patients. We will report the odds ratios with corresponding confidence intervals for the main effect. The main effect will be tested at a two-sided 5% significance level. Sensitivity analyses will adjust for patient age, gender, comorbidities, antiplatelet drug at study entry, and clustering at the nurse level.

For patients who were unable to be contacted by phone for the week 7-10 phone call (lost to follow up), or who declined to participate, we will perform exploratory analyses to determine whether they differed (with respect to demographic characteristics, medical history, or target clinician specialty) from patients who were able to be reached. We will use multiple imputation to account for any missing data for the patients lost to follow up considering all demographic, medical history and target clinician specialty variables considering the data missing at random and combine results across imputation via Rubin's rules. Best and worst case sensitivity

analyses will assess the robustness of the findings and provide the range of uncertainty of conclusions made. For patients who call back the research team after week 10, the survey will still be completed, but their outcome will be considered missing and imputed in primary analysis with a sensitivity analysis using the week 10 outcome.

Patients who reported at the week 7-10 phone call that they were either not using antiplatelet therapy at the start of the trial or were using a PPI will be included in the primary ITT analysis. We expect those who were not initially eligible to be balanced across the groups, thus the comparison of CNNF vs usual care will remain valid; however, for more accurate estimates, we will also conduct a per-protocol analysis where we exclude these individuals.

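### The objective and sample size concern a difference in proportions, but 11.5 plans inference only on a clinician-conditional odds ratio, which may be unstable or undefined if clustering is as strong as 11.1 assumes

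*Combined protocol and SAP*

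**What the plan says.** The primary objective (synopsis, 2.2 and section 4) asks how far the arms differ in the proportion of patients with medication optimization, and 11.4 states the hypothesis as a probability. Section 11.1 expects 5% with usual care and 35% with CNNF and sizes the trial accordingly: "For 90% power to detect the 30% difference between interventions". On clustering it says "we therefore assumed a high-level of correlation in the outcome for patients within clinician clusters (ICC=0.95", citing pilot variation in whether clinicians answered the notifications, with "an average of 2 participants per clinician" and a cap of 4. It also says "We will assume a 20% dropout or ineligibility rate".

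Section 11.5 then says "We will use generalized linear mixed effects modeling (logit link) to estimate the odds of medication optimization at week 7-10". The model has fixed effects for arm, specialty and size, and a random clinician effect. The result is given as "We will report the odds ratios with corresponding confidence intervals for the main effect", and "The main effect will be tested at a two-sided 5% significance level". No estimator, form of test or rule for non-convergence is named. Missing calls are multiply imputed "considering all demographic, medical history and target clinician specialty variables" and pooled by Rubin's rules. Section 11.3 gives proportions by arm as descriptive statistics, and 11.6 uses a similar mixed model for the secondary endpoint.

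**The concern.** There are two linked problems. First, the planned inference is not on the scale of the question. A reader would get arm proportions without an interval for their difference, and an odds ratio with an interval that cannot be read as 5% versus 35%. This holds at any realistic ICC.

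Second, a mixed model learns its random-effect variance from clinicians whose patients have different outcomes. With about 2 patients per clinician and very strong clustering, almost no clinician is like that. The likelihood is then nearly flat, or keeps rising, as the variance grows, and the conditional odds ratio grows with it. The headline figure would depend on a fitting choice that the plan leaves open until the data are in hand.

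**Working it through.** **Sample size (11.1).** Inputs: 5% and 35%, two-sided 5%, 90% power, ICC 0.95, mean cluster size 2, CV 0.62.
- Unpooled patients per arm: (1.960 + 1.282)² × (0.05×0.95 + 0.35×0.65) / 0.30² = 32.1.
- Design effect: 1 + ((0.62² + 1)×2 − 1)×0.95 = 2.68.
- 32.1 × 2.68 = 86.06 per arm, or 43.03 clinicians, rounded up to 44. That is 176 patients, and 176/0.8 = 220.

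The plan's figures reproduce. This design effect treats the ICC as a correlation of the 0/1 outcomes, that is, on the proportion scale, although 11.1 does not name the scale.

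**The odds ratio is not the sized effect.** Marginal OR: (0.35/0.65)/(0.05/0.95) = 10.2. With a normal random intercept on the logit scale and the same two marginal rates, numerical integration gives conditional ORs of 15.5, 25.5 and about 27,400 at latent-scale ICC 0.3, 0.5 and 0.95.

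**Expected clinicians with mixed outcomes.** Two patients of one clinician differ with probability 2p(1−p)(1−ICC). At proportion-scale ICC 0.95 this is 2×0.35×0.65×0.05 = 0.023 for CNNF and 2×0.05×0.95×0.05 = 0.005 for usual care. For the whole trial I assume 55 clinicians per arm, beta-binomial outcomes, and cluster sizes 1-4 with probabilities 0.5325/0.1712/0.06/0.2363 (chosen to give mean 2.00 and CV 0.62).
- No missing calls: 0.87 (CNNF) + 0.18 (usual care) = 1.05 expected. Chance of none: (1 − 0.87/55)^55 × (1 − 0.18/55)^55 = 35%.
- 20% missing: 0.81 expected, 44% chance of none. Treating the whole 20% as missing calls is an assumption, since 11.1 says dropout or ineligibility.

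With no mixed clinician, the likelihood keeps rising with the random-effect variance and no finite maximum-likelihood OR exists. The chance of none under other assumptions (no missing calls to 20% missing):

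| Assumption | Chance of none |
|---|---|
| Proportion-scale ICC 0.95, both arms | 35-44% |
| Proportion-scale ICC 0.9, both arms | 12-19% |
| 0.95 in CNNF, 0.5 in usual care | 7-12% |
| 0.95 in CNNF, 0.1 in usual care | 1-4% |
| Latent-scale ICC 0.95 (4.5 to 3.5 mixed clinicians) | 1-3% |
| Proportion-scale ICC 0.7, both arms | under 1% |
| Proportion-scale ICC 0.5, both arms | about 0 |

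**Dependence on the fitting method.** In 300 simulated trials at proportion-scale ICC 0.95, quadrature maximum likelihood gave a median OR above 10^12, with the random-effect SD at its cap of 25 in 62% of fits. Penalised quasi-likelihood (PQL) on the same trials gave a median of 16 (10th-90th percentile 5-63). At ICC 0.5 (200 trials) the medians were 125 and 14. In one further dataset, moving the SD from 12 to 80 changed −2 log-likelihood by about 1 or less. The log OR went from 18.7 to 120, while the implied risk difference stayed at 0.377-0.380. The data therefore identify the risk difference well and the conditional OR hardly at all.

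**Tests at ICC 0.95.** Complete-case Wald power was about 1% (quadrature) or 92% (PQL). A likelihood-ratio test of the planned model had 99% (null rejection 5.5%, 200 trials). A clinician-clustered risk difference, pooled over imputations that include arm and clinician, averaged 0.30 with 94.9% power, 94.0% coverage and 4.1-5.4% null rejection (3,000 trials per case). These runs assumed outcomes missing completely at random and one ICC for both arms.

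**Imputation variables.** With only the listed variables, the mean risk difference fell to 0.24 and coverage to 89.5%. With arm but not clinician, coverage was 91.9%.

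**The case against.** The strongest reply is that ICC 0.95 is a cautious sizing input, not a forecast. Its stated reason is whether clinicians respond to a message that usual-care clinicians never receive, so it speaks to the CNNF arm only. The outcome also depends on what each patient does. This stands, and it is why the chance of an undefined odds ratio runs from about 0 to 44%. The 27,400 and the 35-44% must also not be combined: the first is at latent-scale 0.95, where the chance of none is only 1-3%.

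A reader might infer that the primary test will miss the effect, or that it must move to a risk difference. The documents do not support either. Section 11.5 names no test. Rubin's rules lead naturally to a Wald test but do not require one, and a likelihood-ratio test of the planned model keeps its power. A reader might also infer that two commercial programs would disagree this widely; the fits here used purpose-written code, and the 10^12 reflects the cap placed on the SD.

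An odds ratio is a conventional measure, it shares its null with the hypothesis in 11.4, and 11.3 will show absolute rates. That too is fair, but it leaves the stated objective without an interval. On imputation, the wording does not exclude arm or clinician; it only fails to name them.

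**Conclusion.** The mismatch is plain from the text: objective and sizing on the proportion scale, inference only on a clinician-conditional odds ratio. It does not depend on the ICC being 0.95. The instability is conditional. It is serious if clustering is near 0.95 on the proportion scale in both arms (35-44% chance of no finite estimate). Non-existence is unlikely on the latent-scale reading and negligible at ICC 0.7 or below, although fitting methods still differed at 0.5. These chances rest on the assumed cluster sizes and the beta-binomial or logit-normal model. The null hypothesis, the sample size and the choice of a mixed model are not at fault, and loss of power is not shown. This should be fixed before analysis.

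**What to change.** In 11.5 and 11.6, report a marginal risk difference with a 95% CI beside the odds ratio, and name it as the estimate that answers the objective. It could be standardised from a model, or come from regression on arm and the two stratification factors with small-sample-corrected standard errors clustered by clinician. For the primary endpoint, pool it over the imputations. The missing-call issue does not carry over to 11.6, because 8.3 keeps chart review for patients who are not reached.

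Keep the mixed model. Label its odds ratio clinician-conditional, and state in advance the estimator, a likelihood-ratio test in place of Wald, and one fallback for non-convergence or zero events in an arm, such as a clinician-level permutation test within strata. Name arm and clinician in the imputation model.

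The cost is SAP wording and a modest amount of extra code, including a clinician term in the imputation. No further patients or data are needed.

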2.2 Objectives

Primary Objective: To determine the extent to which clinician notification with nurse facilitation (CNNF) versus usual care is associated with differences in the proportion of patients who have medication optimization (defined as either discontinuation of all antiplatelet drugs or initiation and adherence to a PPI based on self-report) at week 7-10.

Secondary Objectives: To determine the extent to which CNNF (vs usual care) is associated with differences in the proportion of patients who are recommended to have medication optimization based on chart review after 6 weeks.

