6.6 Strategies for Recruitment and Retention

This trial will be conducted as a pragmatic quality improvement initiative in partnership with the Michigan Medicine anticoagulation monitoring service. There will therefore not be a formal recruitment process. No strategies will be used for participant retention.

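### The imputation variables listed in section 11.5 omit arm and clinician; if the list is followed as written, the primary odds ratio is biased toward no effect

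*Combined protocol and SAP*

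**What the plan says.** Section 11.5 defines a logit mixed model for the primary endpoint: "This model will include fixed effects for CNNF (vs. usual care), target provider specialty and size, and a random effect for clinician". It then commits to the estimate as well as the test: "We will report the odds ratios with corresponding confidence intervals for the main effect".

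The same section holds the only imputation text in the plan. Outcomes of patients not reached are multiply imputed, "considering all demographic, medical history and target clinician specialty variables considering the data missing at random", and combined by Rubin's rules. For patients who call back after week 10, "their outcome will be considered missing and imputed in primary analysis with a sensitivity analysis using the week 10 outcome". Imputed values therefore enter the primary estimate. Best-case and worst-case analyses are planned as sensitivity analyses.

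On how much may be missing, section 6.6 says "No strategies will be used for participant retention", and section 11.1 says "We will assume a 20% dropout or ineligibility rate", one figure for two causes. Section 9.2 allows up to three call attempts over 4 weeks, without remuneration. Under section 8.1, patients who stop warfarin or leave the service after delivery are not phoned.

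**The concern.** An imputation model should contain at least the terms of the analysis model it feeds. Of the primary-model terms, the list names only specialty. Randomisation makes baseline variables uninformative about arm, so none of the listed variables can replace it. An analyst who uses only the list imputes both arms from the same distribution, which mixes a no-effect portion into the data in proportion to the missing share.

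Leaving out the clinician effect has a second consequence. Section 11.1 assumes an ICC of 0.95, and the primary model estimates a clinician-conditional odds ratio. Imputed values that ignore clinician dilute the within-clinician correlation and so pull that odds ratio down as well.

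The primary objective in section 2.2 is about size: "To determine the extent to which clinician notification with nurse facilitation (CNNF) versus usual care is associated with differences in the proportion of patients". An estimate and interval shifted toward zero would understate what the clinic needs in order to judge whether the nursing effort is justified.

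**Working it through.** **Inputs.** From section 11.1: 5% usual care, 35% CNNF, two-sided 5%, 90% power, ICC 0.95, mean 2 patients per clinician, CV 0.62, 20% dropout or ineligibility. The missing-outcome share is not given separately, so 5–30% is an assumption.

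**The plan's own figure.** Unpooled two-proportion formula: (1.960 + 1.282)² × (0.05×0.95 + 0.35×0.65) / 0.30² = 32.11 per arm. Design effect: 1 + ((0.62² + 1)×2 − 1)×0.95 = 2.680. Product: 86.06 patients, hence 44 clinicians per arm and 176 patients; 176/0.8 = 220. The plan's sample size is reproduced.

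**Closed form, arm omitted.** With equal missing share m and non-predictive covariates, the imputed rate is (0.05 + 0.35)/2 = 0.20 in both arms. Each arm's rate becomes (1 − m)p + 0.20m, so RD = (1 − m) × 0.30. At m = 0.20: 0.8×0.05 + 0.04 = 0.08 and 0.8×0.35 + 0.04 = 0.32; OR = (0.32/0.68)/(0.08/0.92) = 5.41. With nothing missing, OR = (0.35/0.65)/(0.05/0.95) = 10.23.

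| Missing | Rates | RD | Marginal OR |
|---|---|---|---|
| 0% | 5.0% / 35.0% | 0.300 | 10.23 |
| 5% | 5.75% / 34.25% | 0.285 | 8.54 |
| 10% | 6.5% / 33.5% | 0.270 | 7.25 |
| 20% | 8.0% / 32.0% | 0.240 | 5.41 |
| 30% | 9.5% / 30.5% | 0.210 | 4.18 |

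Unequal missingness (usual care/CNNF 10%/30% or 30%/10%) gives RD 0.236 and OR 6.34 or 4.54.

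**Missingness that depends on a predictive covariate.** Binary covariate, prevalence 0.5; usual care 2.5%/7.5%, CNNF 20%/50%; missing 5%/35% or the reverse (mean 20%). The list as written gives RD 0.22–0.26 and OR 4.6–6.5; complete cases give 0.28–0.32 and 10.0–10.5. With a stronger covariate (1%/9% and 10%/60%), complete cases can miss the RD by more than the list does (0.339 against 0.271, true 0.30). Not imputing is therefore not better in general.

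**Trial-size simulation, risk difference, ICC 0.95.** 55 clinicians per arm, 1–4 patients each (mean 2.0, CV 0.61), missing completely at random, Rubin's rules, cluster-robust variance, at 10/20/30% missing:

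- List as written: 95% CI coverage 92/89/79%; power 94/91/87% (complete cases 95/95/94%).
- Arm and clinician included: RD 0.300/0.295/0.297; coverage 94/94/94%.
- Null rejection with the list as written (20% in both arms): 1.3–4.4% across ICC 0.2–0.95.

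A second simulation, using a cluster-robust marginal odds ratio at ICC 0.95 and 20% missing, gave a median OR of 5.62 without arm and 10.70 with arm.

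**Trial-size simulation, mixed model.** Random-intercept logistic with arm as the only fixed effect, marginal rates 5%/35%, 500 trials per cell. Section 11.1 does not state the scale of its ICC, so clinician SDs of 1 and 2 on the logit scale were assumed; latent ICC = SD²/(SD² + 3.29). The last column is coverage with arm and clinician in the imputation. Entries are at 10/20/30% missing:

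| Latent ICC | True conditional OR | Median OR, list as written | Coverage, list as written | Coverage, both terms |
|---|---|---|---|---|
| 0.23 | 13.8 | 9.1 / 6.6 / 4.8 | 90 / 78 / 54% | 97 / 98 / 97% |
| 0.55 | 30.2 | 13.8 / 8.4 / 5.5 | 81 / 58 / 24% | 93 / 93 / 95% |

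**Arm without clinician.** In a large-sample run with fitted clinician SD 1.7 and 20% missing, the conditional log odds ratio is 3.20 on full data, 2.77 with arm only in the imputation, and 2.00 with neither term.

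**Size.** With arm included and size omitted, RD bias is 0 if missingness does not depend on size, and 0.006–0.013 in adverse cases.

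**The case against.** The best defence is about reading. The sentence just before the imputation text compares patients reached and not reached on the same three groups of variables. The list may therefore be only the predictors of missingness that support the missing-at-random assumption, added to a model that already holds arm and clinician. Nothing excludes arm. That reading is possible, but the text does not secure it. Specialty is itself a primary-model term and is named, while arm, size and clinician are not.

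It is also fair that the literal reading does not inflate false positives and costs little power at the planned effect, so the conclusion of the hypothesis test would rarely change. That stands. The best/worst-case and late-caller analyses show a range but leave the primary odds ratio as it is.

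The mixed-model figures rest on assumed clinician SDs well below what an ICC of 0.95 would imply. At a latent ICC of 0.95 the conditional odds ratio has no usable benchmark. Those figures are illustrative; the closed form and the risk-difference coverage are the firmer results. The missing share is unknown, and with three call attempts it could be below 20%; even at 5% the marginal odds ratio falls from 10.2 to 8.5.

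Last, the remedy asks for multilevel imputation with few usual-care events. That is a real difficulty, and the reason for a fallback stated in advance.

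**Conclusion.** The concern holds, on its stated condition. The plan's only imputation list does not name arm, size or a clinician effect. Followed as written, it biases the primary odds ratio and its interval toward no effect whenever there is a true effect and outcomes are missing. At the planned rates and 20% missing, the marginal odds ratio is 5.4 instead of 10.2 and the risk difference 0.24 instead of 0.30. Risk-difference interval coverage at ICC 0.95 is about 89%.

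This rests on three assumptions: a missing share within 5–30%; baseline variables that cannot stand in for arm, as randomisation implies; and, for the simulations, missingness unrelated to outcome. Omitting arm drives the marginal bias. Omitting clinician adds to the bias in the mixed-model odds ratio. Omitting size matters little. It should be fixed before analysis, but it does not threaten the validity of the test.

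**What to change.** State in section 11.5 that the imputation model includes every term of the primary model (arm, specialty, size and a clinician effect) plus the variables already listed. Name in advance a convergence criterion and a fallback, for example the planned mixed model fitted to observed outcomes.

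Arm and clinician must be added together. Arm without clinician, which the plan does not propose, gives type I error of 6.7/7.9/11.5% at 10/20/30% missing and ICC 0.95; a repeat gave 6.4/7.4/8.4%. It is 6.5/7.0/8.6% at ICC 0.5 and 5.6/6.5/6.4% at ICC 0.2. With both terms at ICC 0.95 it is 5.5/5.9/5.7%.

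The cost is one or two sentences and modest programming, with data already collected. Convergence is the main risk: 5% of 110 is 5.5 usual-care events, of which about 4.95/4.4/3.85 would be observed at 10/20/30% missing. If the sponsor already intends this model, stating it settles the point.
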